## 5 STUDY RATIONALE

Non-melanoma skin cancers, BCC and SCC, are the most prevalent of all skin cancers. Multiple publications have shown that radiation therapy using kilovoltage X-rays is a viable option for the treatment of BCC and SCC but treatment must be individualized to determine if radiation therapy should be an adjuvant therapy following surgical resection or if the radiation therapy is the primary treatment for skin cancer. Local recurrence rate varies depending on the histology, BCC versus SCC. SCC has a higher recurrence rate than BCC; deaths have been attributed to the recurrence of SCC.

Brachytherapy has the advantage of delivering a high dose to the tumor while sparing the surrounding normal tissues. With proper case selection and delivery technique, high-dose rate (HDR) brachytherapy has great promise, allows short treatment times, and can be performed on an outpatient basis. The Xoft Axxent Electronic Brachytherapy (eBx) System allows for the administration of high dose rate brachytherapy treatments using an electronic source. The Xoft Axxent System Controller and Source are cleared by the United States Food and Drug Administration to deliver high dose rate X-ray radiation for brachytherapy.

A matched pairs study was completed previously comparing eBx treatment outcomes to Mohs surgery outcomes. The median follow-up was three years. Local recurrence, toxicities, and cosmesis were the endpoints. Because of the excellent cosmetic outcomes evident in this study at three years, the physicians rated cosmesis as “excellent” or “good” in 97.6% of EBx-treated

lesions, and 95.7% of MMS-treated lesions, cosmetic outcomes in this study will not be collected. It is most important to understand the long-term recurrence rates for this treatment option. The rationale for this retrospective data collection study is to understand longer-term outcomes in patients treated with eBx for the treatment of both BCC and SCC NMSC.

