## **7 STUDY DESIGN, ENROLLMENT, AND DURATION**

### **7.1 Study Design**

This is a retrospective-prospective study design. The study is post-market, on-label observational study for the treatment of NMSC. Patients who completed treatment at least five years from the last treatment will be identified and existing data as required by this protocol in the patient's record will be collected in addition to conducting office visits or telehealth visits (video) for long-term follow-up.

The study will include:

Identifying patients, retrospectively, who completed treatment a minimum of five years from the last treatment. The history and demographic data will be collected from up to 300 subjects previously treated with eBx for the treatment of NMSC. Patients will have an office visit or telehealth visit in order for the investigators to assess the lesion site, document absence of recurrence, treatment for recurrence (if applicable), and long-term toxicities at the time of the prospective visit.

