## 7.6 Eligibility Criteria

**7.6.1 Inclusion Criteria** All answers must be YES to have lesions included in this study.

1. Previously completed treatment for non-melanoma skin cancer using Xoft eBx Electronic Brachytherapy System according to standard of care;
2. Provides informed consent;
3. Greater than 40 years of age;
4. Pathological diagnosis confirmed to be squamous cell carcinoma, or squamous cell carcinoma-in-situ, or basal cell carcinoma prior to treatment;
5. Cancer Staging included in this study:
  - Stage 0: Tis, N0, M0
  - Stage 1: T1a, b, c, N0, M0
  - Stage 2: T2a, N0, M0

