### 7.6.2 Exclusion Criteria

All answers must be NO to have lesions included in this study.

1. Target area is adjacent to a burn scar;
2. Any prior definitive surgical resection of the cancer, prior to Radiation Treatment;
3. Known perineural invasion;
4. Actinic Keratosis;
5. Known spread to regional lymph nodes;
6. Known metastatic disease;
7. Lesion treated with Mohs surgery.

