## 8 METHODOLOGY

### 8.1 Identifying the Population

The first phase of this study will be to identify patients who completed treatment with eBx at least five years ago prior to study onset and collect history and demographic data, and eligibility data retrospectively from the patient records and on source worksheets.

This phase will include a review of the site's medical records to determine if the source documentation contains the variables that are needed to determine eligibility, and which will be used in the endpoint analyses.

These variables include:

Patient Age

Pathology report for evidence of:

- o Lesion size (cm) / TNM stage
- o Lesion diagnosis (BCC, SCC)

Last treatment date for each location

Lesion location (e.g. face, extremities, neck, nose, scalp, torso)

Data Collected Prospectively:

Recurrence of cancer at prospective follow-up visit

Recurrence occurred prior to prospective follow-up visit

Long term skin toxicity (graded according to CTCAE v.5)

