## **11 STUDY MANAGEMENT**

### **11.1 Site Requirements and Selections**

Study sites will be those that previously participated in the matched pair study with a retrospective-prospective study design. Sites will be associated with and under the approval of an Institutional Review Board (IRB) [45 CFR 46.10(b)]

Sites selected have expressed an interest in the conduct of a controlled study to collect and report long-term outcomes of eBx for the treatment of non-melanoma skin cancer. Each site will execute a clinical trial agreement with the sponsor. The contract will be executed prior to first subject enrollment at the site.

Case report forms will be used to collect data for the prospective visits. These will also be considered source documentation for data not in the patient medical record.

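### Exclusion 7 (Mohs surgery) carries no time reference, so read literally it removes an eBx lesion that recurred and was then treated with Mohs

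*Combined protocol and SAP*

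**What the plan says.** The exclusion list in section 7.6.2 applies lesion by lesion: one YES removes the lesion. Item 7 is "Lesion treated with Mohs surgery", with no date or sequence. Item 2 in the same list does carry one: "Any prior definitive surgical resection of the cancer, prior to Radiation Treatment". It is the only one of the seven items that does. Items 3 (perineural invasion), 5 (regional nodal spread) and 6 (metastatic disease) are undated as well.

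The first inclusion criterion requires "Previously completed treatment for non-melanoma skin cancer using Xoft eBx Electronic Brachytherapy System according to standard of care". Section 8.1 has sites find patients who finished eBx five or more years before study onset and "collect history and demographic data, and eligibility data retrospectively from the patient records". Table 1 in section 13.1 places the eligibility form under the chart review and the local recurrence form under the prospective visit.

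The plan also means to capture past failures. Section 8.1 lists "Recurrence occurred prior to prospective follow-up visit" among the data items, and section 7.1 asks the investigator to document any treatment given for a recurrence. The primary endpoint (section 7.4) is absence of local recurrence at five years or later.

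**The concern.** By the time item 7 is answered, the chart can hold five or more years of events after eBx. If a lesion recurred and the recurrence was treated with Mohs, the honest literal answer to item 7 is YES. The lesion is then excluded at chart review, before the recurrence form is reached. Eligibility would be decided by the outcome that the study sets out to measure.

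Section 13.2 states that the study is not powered and exists to report the number and percent with a recurrence, so that percentage is the result. The plan contains no analysis that would reveal or correct the loss, and no count of exclusions by reason. Sites that read the item differently would also screen differently, and their data would be pooled.

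**Working it through.** **1. What item 7 can act on.** There are three possible timings.

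- *Mohs instead of eBx.* The lesion already fails inclusion 1.
- *Mohs before eBx.* The lesion may already fail item 2, if a site counts Mohs as definitive resection. Section 4 lists Mohs separately from conventional surgery, so a site might not. Item 7 then has an ordinary baseline use.
- *Mohs after eBx.* No other item addresses this. Read literally, item 7 excludes the lesion, including when the Mohs was for a recurrence.

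**2. Whether another section limits it.** Sections 7.1 and 8.1 show an intent to keep lesions with an earlier recurrence, but neither qualifies the exclusions, and a lesion that fails eligibility is not in the study. Section 8.2 makes screening before contact explicit only for patients outside the prior studies; prior-study patients are called from a list. A YES to item 7 excludes the lesion in either group.

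**3. Direction, at lesion level.** Let p be true recurrence and m the share of recurrences that are excluded. Each excluded recurrence leaves the count of recurrences and the denominator:

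reported recurrence = p(1 − m) / (1 − pm)

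Because p ≤ 1, 1 − m ≤ 1 − pm, so the result never exceeds p.

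**4. Illustrative size.** The plan has no figure to reproduce, and the documents give neither p nor m for eBx. All values here are assumptions. Section 4 offers only loose anchors from other modalities: 98% five-year control in a surface-mold Ir-192 series (p = 2%), and 91% as the low end of a range by tumor size with superficial X-ray (p = 9%). The values of m have no source.

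| p | m = 0 | m = 10% | m = 25% |
|---|---|---|---|
| 2% | 2.00% | 0.018/0.998 = 1.80% | 0.015/0.995 = 1.51% |
| 5% | 5.00% | 0.045/0.995 = 4.52% | 0.0375/0.9875 = 3.80% |
| 9% | 9.00% | 0.081/0.991 = 8.17% | 0.0675/0.9775 = 6.91% |

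At p = 5%, freedom from recurrence would be reported as 95.5–96.2% instead of 95.0%.

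In whole lesions, assuming 300 lesions (one per subject) with 15 recurrences: 15/300 = 5.0% (exact 95% interval 2.8 to 8.1). Dropping 4 of the 15 gives 11/296 = 3.7%.

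**5. Subject level.** Section 7.2 lets a subject contribute as many as three lesions. If all of a subject's recurred lesions are excluded, the subject either leaves the analysis or stays in, recurrence-free, on another lesion. Take p and m at subject level, and let s be the share of affected subjects who stay in:

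reported recurrence = p(1 − m) / (1 − pm(1 − s))

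At p = 5% and m = 10%, this is 4.52% (s = 0) to 4.50% (s = 1). At m = 25%, it is 3.80% to 3.75%. A subject with another recurred lesion that is retained remains a failure. The reported rate therefore falls or is unchanged here too.

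**6. Retention alone is not enough.** Sections 7.4 and 13.2 do not say how a recurrence that was treated before the visit is scored. A lesion cleared by surgery could be kept and still be recorded as free of recurrence at the visit.

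**The case against.** The strongest reply is that the list describes the lesion as it stood at eBx treatment. Inclusion 4 refers to pathology before treatment, inclusion 5 gives N0/M0 staging, and section 4 says that primary radiation was selected for the patients whose data will be collected. Item 7 would then screen out Mohs followed by eBx. It could also be guarding against comparison lesions: section 5 says "A matched pairs study was completed previously comparing eBx treatment outcomes to Mohs surgery outcomes", and section 11.1 says "Study sites will be those that previously participated in the matched pair study with a retrospective-prospective study design". This is plausible and may well be the intent. No section states it, however, and the site staff answering the form have only the wording.

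A reader might infer that item 7 can bite only on Mohs after eBx, because inclusion 1 and item 2 cover everything else. The documents do not support that: item 2 need not cover Mohs, and overlapping eligibility items are common. Nor is the missing date peculiar to item 7. Items 3, 5 and 6 share it, and read literally they could remove a lesion whose recurrence later spread. That part of the objection stands and widens the fix.

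It is also fair that few patients may be affected. Section 4 describes people for whom resection was not an option, so m may be low. But that passage concerns the choice of initial treatment and does not rule out Mohs after a recurrence.

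**Conclusion.** The concern holds as a one-directional risk that the wording permits. Item 7 as written lets a site exclude an eBx lesion because it failed and was treated with Mohs. This can only raise reported freedom from recurrence or leave it unchanged, and it conflicts with sections 7.1 and 8.1.

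A reader might go further and conclude that the criterion was designed to remove failures, or that the result will be biased. The documents support neither. They do not show that any site reads the item this way, and the recurrence items point to the opposite intent.

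The size is unknown and is zero if no recurrence was treated with Mohs. Under the assumed 5% recurrence and 10–25% exclusion, the lesion-level shift is 0.5 to 1.2 percentage points. That is well inside the sampling interval for 15/300, but it always favours the device. Because the correction is short and protects the primary result, it should be made.

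**What to change.** - State that exclusions 3, 5, 6 and 7 refer to the lesion's status and treatment up to the start of eBx. Item 7 would become: *Lesion treated with Mohs surgery before eBx.*
- Add that surgery for a recurrence after eBx, or spread of such a recurrence, does not exclude the lesion, and that the recurrence is counted as a recurrence in the primary analysis.
- Report the number of lesions excluded under these four items, split by whether the event came before or after eBx.
- Re-screen any lesion already excluded for a post-eBx event.

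The cost is a short wording change in the protocol and the eligibility case report form, plus one count in the report. Re-screening is needed only if such exclusions have been made. The local control figure may come out slightly less favourable.

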## 8 METHODOLOGY

### 8.1 Identifying the Population

The first phase of this study will be to identify patients who completed treatment with eBx at least five years ago prior to study onset and collect history and demographic data, and eligibility data retrospectively from the patient records and on source worksheets.

This phase will include a review of the site's medical records to determine if the source documentation contains the variables that are needed to determine eligibility, and which will be used in the endpoint analyses.

These variables include:

Patient Age

Pathology report for evidence of:

- o Lesion size (cm) / TNM stage
- o Lesion diagnosis (BCC, SCC)

Last treatment date for each location

Lesion location (e.g. face, extremities, neck, nose, scalp, torso)

Data Collected Prospectively:

Recurrence of cancer at prospective follow-up visit

Recurrence occurred prior to prospective follow-up visit

Long term skin toxicity (graded according to CTCAE v.5)

## **8.2 Long-term Follow-up Visits**

Patient Selection: Patients who are due for their annual skin assessment with a minimum of five years since their last eBx treatment will be selected to call for an appointment. The patients who were in prior studies will be called from a list kept at the study sites. Additional patients who were not in the previous studies will be contacted if they meet eligibility criteria. The patient will be told about the study and asked if they would be willing to participate in the Xoft study through an on-site or remote telehealth appointment.

On-site Visits: Patients agreeable to participating that return for an office visit for prospective data collection will be offered \$100.00 compensation for his/her time and effort required to participate in this study. Written informed consent will be required for participation in the study.

Remote Visits: Patients agreeable to participating that choose a remote visit by video, such as Zoom or Web-Ex or another video conference platform will be offered \$100.00 compensation for his/her time and effort to participate in this study. Verbal informed consent documented by the study staff will be required for participation in the study. Signed informed consent will be waived.

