## 2 PROTOCOL SYNOPSIS

STUDY NAME	A Post-market Multi-Center Retrospective-Prospective Study to Assess Long-term Clinical Outcomes of Non-melanoma Skin Cancer Patients Treated with eBx
PRINCIPAL INVESTIGATOR	[name], FACR
SITES	Up to 5 sites will participate
STUDY DESIGN	
This is a retrospective-prospective post-market, on-label, observational study. Patients who completed eBx treatment <math>\geq</math> 5 years ago since final treatment will be identified and any existing data in the patient's record will be collected in addition to conducting follow-up visits for long-term follow-up. The study will include 2 parts:
 
 
1. Retrospective Chart Review: Collect data from patient records who completed eBx treatment a minimum of five years prior to study onset. The history and demographic data will be retrospectively collected from up to 300 subjects previously treated with eBx for the treatment of NMSC.
 
2. Prospective Follow-up: Patients will either return for a minimum of five-year long-term follow-up visits or telehealth (video) for the investigators to assess the lesion site, document absence/presence of local recurrence and long-term skin toxicities after treatment.
 

SAMPLE SIZE	Up to 300 patients will return for follow-up a minimum of five years post eBx treatment.
STUDY OBJECTIVES	
 
1. To evaluate local recurrence of eBx treated lesions in subjects with a minimum of five-year follow-up.
 
2. Assess long-term skin toxicities.
 

PRIMARY EFFECTIVENESS ENDPOINT	Absence of local recurrence at $\geq$ 5-year follow-up at treatment site(s).
SECONDARY SAFETY ENDPOINT	Occurrence of long-term skin toxicities.
ESTIMATED STUDY PERIOD	Follow-up Visits: Estimated to occur over 6 months.
SPONSOR & FUNDING PARTY	
Xoft, Inc., a Subsidiary of iCAD, Inc.  [name]  [name]

STATISTICAL ANALYSES, STUDY MANAGEMENT, EDC, MEDICAL WRITING	
Eminence Clinical Research, Inc.  [name]  [name]  [name]

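### Section 8.2 counts five years from the patient's last eBx, so a recurrence re-treated with eBx within five years removes the patient, while the lesion-level criteria have no time rule and no index course is defined

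*Combined protocol and SAP*

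**What the plan says.** The five-year rule appears in four places, always as a rule about patients:

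- Synopsis, study design: patients at least "5 years ago since final treatment will be identified"; the chart-review part reads "Collect data from patient records who completed eBx treatment a minimum of five years prior to study onset".
- Section 7.1: "Patients who completed treatment at least five years from the last treatment will be identified".
- Section 8.1: the first phase is to "identify patients who completed treatment with eBx at least five years ago prior to study onset".
- Section 8.2, the recruitment step: patients "with a minimum of five years since their last eBx treatment will be selected to call for an appointment".

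Eligibility is applied to lesions. Section 7.6.1 opens with "All answers must be YES to have lesions included in this study", and its only treatment criterion is "Previously completed treatment for non-melanoma skin cancer using Xoft eBx Electronic Brachytherapy System according to standard of care". It gives no minimum time. The exclusions in 7.6.2 give none either and do not mention repeat eBx. Section 7.2 allows up to three lesions per subject, and 13.2 reports results by subject and by lesion.

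Section 8.1 collects "Last treatment date for each location" and, prospectively, whether a recurrence occurred before the follow-up visit. Sections 7.3, 7.4 and 13.2 all place the outcome at five years or more. No section says which eBx course starts the clock when a site was treated more than once.

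**The concern.** Selection under 8.2 depends on something that happens after the treatment being evaluated. A patient can have a lesion with eight years of follow-up and still not be called because eBx was given two years ago. If the later course was for a recurrence at the same site, the event that the primary endpoint is meant to count is also the event that takes the patient out of the study. Dropping failures can only lower the recurrence percentage. The study is descriptive and has no comparison group, so nothing offsets that error.

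The wording also leaves room for other readings. Up to five sites may take part, and each could apply a different clock.

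**Working it through.** The plan has no computed figure to reproduce: 13.2 states that the study is not powered, and 300 is a cap. The check is a reading of the text, followed by an illustration on assumed inputs.

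**Step 1. Different sites treated at different times.** Take a patient with three lesions last treated 8, 7 and 2 years ago, within the three-lesion limit of 7.2.

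| Reading | Lesions that enter |
|---|---|
| A. Five years since the patient's last eBx at any site (8.2 as written) | None; the patient is not called |
| B. Patient qualifies on one lesion, then the 7.6 lists are applied | 8, 7 and 2 years |
| C. Five-year clock applied to each lesion | 8 and 7 years |

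Reading A loses two long-term lesions but cannot admit a short one, because every eBx lesion of a selected patient is at least five years old. Reading B keeps the long-term lesions but admits the two-year one. A similar gap opens if the additional patients in 8.2, who are contacted if they meet the eligibility criteria, are screened on 7.6 alone. A and B are alternatives and their effects cannot be added.

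**Step 2. Same site treated twice.**

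- First course 8 years ago, recurrence re-treated with eBx 2 years ago. Under A the patient is not called. If the last date at that location is the clock, the lesion has only two years and drops out on that reading too.
- First course 8 years ago, recurrence re-treated with eBx 6 years ago. The patient is called. The recorded date is that of the re-treatment, so the clock restarts at six years. The earlier-recurrence item in 8.1 can still record the failure, but the text does not say how a failure before the last course enters the primary endpoint.

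**Step 3. Size if failures are dropped (assumed inputs).** Let r be the true proportion of patients with recurrence and f the share of those patients removed because of eBx in the last five years. Then

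observed rate = r(1 − f) / (1 − rf).

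With r = 5%:

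- f = 10%: 0.05 × 0.90 / (1 − 0.005) = 0.045 / 0.995 = 4.5%.
- f = 30%: 0.05 × 0.70 / (1 − 0.015) = 0.035 / 0.985 = 3.6%.

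Recurrence-free percentages would read 95.5% to 96.4% against a true 95.0%. With the same f, r = 2% gives 0.018 / 0.998 = 1.8% to 0.014 / 0.994 = 1.4%, and r = 10% gives 0.09 / 0.99 = 9.1% to 0.07 / 0.97 = 7.2%.

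For scale, the exact 95% interval for 15 of 300 (5.0%) is 2.8% to 8.1%. The illustrated shift lies within that interval, but it goes one way only and does not shrink with more patients.

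**Step 4. Size under Reading B instead (assumed inputs).** With 5% recurrence at five years and a constant hazard, risk at t years is 1 − 0.95^(t/5): 1.02% at 1 year and 2.53% at 2.5 years. If 10% of lesions are that short, the observed rate is 0.9 × 5% + 0.1 × (1.02% to 2.53%) = 4.6% to 4.75%. If 20% are, it is 0.8 × 5% + 0.2 × (1.02% to 2.53%) = 4.2% to 4.5%.

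**The case against.** The strongest answer is that 8.2 need not mean the last course at any site. eBx is given as a course, and the last or final treatment can mean the last session of that course; 7.1 and the synopsis are open to this. Section 8.1 lists the date for each location among the variables needed for eligibility and for the endpoint analyses, which supports a per-location clock. The five-year requirement is in the objective and the endpoint, so its absence from 7.6.1 could be called a drafting gap. Section 7.1 also documents treatment for recurrence, and 8.1 records earlier recurrence.

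Much of this stands. Per-location dates would allow a lesion-level clock, and the recurrence item can rescue failures in patients who are called. Two things remain. Neither item exists for a patient who was never called. And the per-location date is the last date, so a site re-treated within five years still falls short of five years.

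A reader might infer that the plan both loses older lesions and admits lesions under five years, so that two downward biases add up. The documents do not support that, because each needs a different reading of the rule (Step 1). Nor do they support a stated size: they give no recurrence rate for this cohort, no repeat-eBx rate and no relative risk for patients treated again.

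**Conclusion.** The concern holds in a limited form. Applying 8.2 as written excludes patients on the primary outcome when a recurrence was re-treated with eBx within five years, and the bias is then toward a lower recurrence rate. For later eBx at another site, the certain loss is of eligible long-term lesions; a bias follows only if such patients also have a different recurrence risk, which is an assumption. Entry of lesions under five years is an alternative consequence under another reading.

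The fall from 5% to about 4.5% to 3.6% rests wholly on the assumed 5% and the assumed 10% to 30% of recurrent patients dropped. It shows direction, not an estimate. The protocol should be changed because the reported percentage is the study's main output and the correction is small.

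**What to change.** Add a per-lesion criterion to 7.6.1: at least five years from the end of the first (index) eBx course at that lesion to one stated reference date. Choose that date explicitly, because the synopsis and 8.1 count to study onset while the outcome is assessed at the follow-up visit.

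Then state three rules:

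1. Later eBx at another site does not exclude a patient's older lesions.
2. Later eBx at the same site does not restart the clock.
3. A lesion re-treated with eBx counts as a recurrence when the record documents that the re-treatment was for recurrence of the index lesion. A new primary in the same area does not count; treating every later same-site course as a recurrence would overstate the rate.

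Collect the index-course date for each location beside the last date, and make the synopsis, 7.1, 8.1 and 8.2 agree with 7.6.1.

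The cost is protocol wording, one more date per location and possibly a slightly higher reported recurrence rate.
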